11.3. Analysis Sets

11.3.1. Intent-to-Treat (ITT) Analysis Set

All randomized subjects will be included in the ITT analysis set. The ITT population will be used for all primary, secondary, and other efficacy analyses. In these analyses, subjects will be classified according to the treatment randomized (not actual treatment received).

11.3.2. Per Protocol (PP) Analysis Set

Patients in the PP analysis must meet all inclusion criteria and no exclusion criteria. All subjects who are included in the ITT analysis set, receive at least 4 doses of study drug/placebo, and did not have major protocol deviations will be included in the PP analysis set. Major protocol violations will be identified prior to the unblinding of the study at the final analysis. Note, patients who die, or are discharged from the ICU before 4 doses can be given will be included in the PP analysis.

11.3.3. Safety Analysis Set

The safety analysis set includes all subjects who are randomized and received at least one administration of study drug. Subjects will be classified according to actual treatment received.

11.4. Final Data Analysis

The final data analysis will be performed after all enrolled subjects have completed follow up. If the trial stops for expected success on the mortality endpoint at N=200, 300, or 400, the final analysis will be based solely on mortality and will require p<0.001. If the trial reaches N=500 or more without predicted success on mortality, indicating more moderate effects, the primary analysis will be based on the more sensitive VVFD endpoint using the remaining 2.4% alpha.

11.4.1. Primary Efficacy Endpoint

The primary efficacy endpoint is vasopressor and ventilator-free days (VVFD) in the first 30 days after start of treatment. The endpoint will be recorded to the nearest day. Subjects who die will be scored zero days, even if there is a period during which the subject is alive and free of vasopressors and mechanical ventilation. Subjects who must return to ventilation and/or vasopressors will have their counters reset at zero days. If the trial reaches N=500 or more, the primary analysis is a Wilcoxon rank-sum test (also known as a Mann-Whitney U test), which will be performed using a one-sided alpha of 0.022. If the study is extended beyond N=500, then the final analysis on VVFD requires p<0.022. This p-value threshold was selected through simulations in order to control type I error and account for the multiple analyses at N=500, 1000, 1500 and 2000.

The primary analysis will be performed on the ITT population. A sensitivity analysis will be performed on the PP analysis set.

For subjects with missing data on the primary endpoint, a "last status carried forward" approach will be used. If a subject was last seen on either vasopressors or mechanical ventilation, it is assumed that the subject remained so, and is imputed to a value of zero VVFD. If the subject was last seen off of vasopressors and mechanical ventilation and is not known to be dead, it is also assumed that the subject remained so in the remainder of the 30-day period.

VVFDs will be tabulated by arm and presented graphically by histograms and cumulative distribution functions.

11.4.2. Key Secondary Endpoint

The mortality endpoint will be tested using a Chi-square test. If the trial stops accrual at N=200, 300, or 400, all subjects will be followed and the primary analysis will be based on mortality, with trial success defined as p<0.001. If the trial reaches N=500 or more, a gatekeeping strategy will be used such that the mortality endpoint will only be tested if the primary endpoint meets success. In that case, the mortality endpoint will be tested with one-sided alpha of 0.024. The mortality test will be performed on the ITT population. A sensitivity analysis will be performed on the PP analysis set.

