6.1. Design Overview

The VItamin C, Thiamine And Steroids in Sepsis (VICTAS) Study is a double-blind, placebo-controlled, adaptive randomized clinical trial designed to investigate the efficacy of the combined use of vitamin C, thiamine and corticosteroids (hereafter "Treatment Protocol" or "TP") versus indistinguishable placebos (hereafter "Control Protocol" or "CP") for patients with sepsis. The trial employs a novel endpoint that approximates a patient's risk of death based on the time spent on vasopressors or receiving respiratory support. Time spent on vasopressors or receiving respiratory support captures a patient's speed of recovery. Mortality rate is a key secondary endpoint for the trial.

The trial has a flexible sample size that will be determined adaptively. The trial will have an initial enrollment target of up to 500 subjects to detect a potential mortality difference of 20%, a conservative estimate based on the 32% benefit observed in the study by Marik, et al. However, if the data are indeterminate on mortality at N=200, 300, or 400 subjects, the trial may continue to a larger sample size (up to 2000) using an adaptive "Goldilocks" strategy based on the primary endpoint of VVFD with assessments at 500, 1000, 1500, or 2000 subjects randomized to either the TP or CP. The overall type I error rate for the trial is controlled at 2.5%. The early interim analyses have conservative rules for spending alpha so that 0.1% will be used up to N=400 and the remaining 2.4% is reserved for N=500 (or beyond). For more detail, please see section on Statistical Considerations below (Section 11).

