Accrual to the trial may stop for expected success on both the primary endpoint of VVFD and mortality. This requires that predictive probability be greater than 95% for detection of a statistically significant beneficial effect on both VVFD (alpha = 0.022) and mortality (alpha = 0.024) at the current sample size. In order to meet this threshold, the data must already be strongly positive, and furthermore, there must be little risk that the subjects with outstanding data might reverse the success once all data becomes available. If this threshold is reached, then no additional subjects will be enrolled. Follow-up of currently enrolled subjects will continue and the final analysis will be conducted after all currently enrolled subjects have been followed to their final outcome.

c.) Stoppage of accrual for expected success on VVFD alone

Accrual to the trial may also stop for expected success on the primary endpoint of VVFD alone. This requires that predictive probability for detecting a statistically significant beneficial effect (at the current sample size) on VVFD exceeds 95% and predictive probability for detection of such an effect on mortality (at the maximal sample size) is less than 10%. Thus, the data must already be strongly positive for VVFD and indicate a low probability that significance can be achieved on mortality, even with additional sample size. If this early stopping threshold is reached, then no additional subjects will be enrolled. Follow-up of currently enrolled subjects will continue and the final analysis will be conducted after all currently enrolled subjects have been followed to their final outcome.

d.) Continue to the next analysis

If no condition for stopping accrual is met at the interim, then the trial will continue accrual to the next analysis time (either the next scheduled interim, or to full enrollment and final analysis). For more detail, please see section on Statistical Considerations below (Section 11).

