6.4. Study Initiation and Expected Trial Duration

The VICTAS Study is expected to begin enrollment in the spring of 2018. Enrollment of 500 subjects is predicted to require approximately 36 months after the first subject is enrolled. A minimum of 20 sites will participate in subject recruitment and enrollment.

7. Study Population

Any patients admitted to a study site hospital who have or subsequently develop sepsis or septic shock associated with cardiovascular or respiratory failure will be considered for enrollment. The site is responsible for screening patients and selecting those who are appropriate for the study based on the defined inclusion and exclusion criteria (section 7.1). Subjects must be randomized within 24 hours of the onset of organ failure (i.e., cardiovascular or respiratory support).

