The diagram below illustrates the individual subject progression for the trial.

- - 9.2. Screening and Informed Consent

Potentially eligible subjects will be initially screened by several methods including clinical team referrals, electronic health record reviews (see HIPPA form 4) or predictive analytic methods (at site where those methods are available). When sepsis is suspected the research team on-call will be immediately notified (using systems established at local sites). The study team will determine if the patient meets the *basic inclusion* criteria for presumptive eligibility (detailed above).

The investigator or designee will respond to the ED or ICU in order to verify patient eligibility based on the full inclusion/exclusion checklist. If the patient meets the basic inclusion criteria, the investigator or designee will review the enrollment criteria with the clinical care team to confirm eligibility. All screen failures will be recorded on the Screen Failure Log. To maintain compliance with recruitment procedures, sepsis admissions should be reviewed weekly by a research team member to determine if any eligible cases were missed and to identify local barriers to enrollment.

It is anticipated that each site will enroll on average 2 subjects per month.

Eligibility Verification: The eligibility CRF must be completed prior to randomization to ensure all inclusion and exclusion criteria have been confirmed. If eligibility questions arise, the CCC/National Hotline should be contacted immediately for clarification.

Informed Consent: Informed consent must be obtained before any study specific procedures are done. The investigator (or designee) will give the subject or subject's legally authorized representative (LAR) information about the trial in a form that they can read and understand. The consent process and date of informed consent given by the subject or the subject's LAR will be documented in the subject's files and carried out in accordance with state and institutional regulations. In the case where the subject is unable

to provide consent, the subject's LAR (in accordance with applicable law) may provide consent for the patient.

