For the primary outcome measure (VVFD), we will use an adaptive strategy with assessments at 500, 1000, 1500, or 2000 subjects randomized to either the TP or CP. When the data are sufficiently strong on the primary endpoint (VVFD), the trial may select a smaller sample size, but when necessary (e.g. for a moderate effect), the trial may continue to a larger sample size.

The overall Type I error rate for the trial is controlled at 2.5%. The early interims at N=200, 300, 400 are designed to conservatively spend alpha so that 2.4% remains for the analysis at N=500 (or beyond).

Anticipated alpha expenditures at all interim analyses, determined through clinical trial simulation, are as follows:

Interim Analysis	Alpha Spend
N = 200	0.0002
N = 300	< 0.0001
N = 400	0.0003
N = 500	0.010
N = 1000	0.0026
N = 1500	0.0033

The power estimates used for sample size selection if the trial progresses to N=500 and beyond were also determined through clinical trial simulation, and take into account both the primary outcome of VVFD and the secondary mortality outcome. Indeed, these two outcomes are inter-related, with our primary efficacy endpoint (VVFD) representing a combination of treatment effect on mortality (all deaths are recorded as zero VVFD) and effect on vasopressor and ventilator support dependence in survivors. Full details of these simulations, over a wide range of assumptions, may be found in a separate document entitled *VICTAS Trial Adaptive Design Report*.

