11.5.1. Statistical Models for the Interim Analysis

At the time of each interim analysis, there will be subjects for whom the final outcome is unknown (e.g. subjects who are enrolled but whose data is not yet available, or future subjects not yet enrolled). To make decisions regarding sample size selection, Bayesian predictive distributions are employed for the multiple imputation of outcomes for such subjects. These models will play no role in the final analysis, but rather are only used to facilitate the early stopping rules at the interims.

Predictive Probabilities for Mortality

To compute predictive probabilities for the mortality endpoint alone, we rely on a Beta-Binomial model, with independent non-informative Beta(0.5, 0.5) priors on each q_j , where q_j is the mortality rate on arm j. Based on this model, we compute:

- PP_{mort} (current N): the predictive probability of success on the mortality endpoint (Chi square test) if enrollment stops at the current sample size, and all currently enrolled subjects are followed to their primary outcome.
- PP_{mort} (max N): the predictive probability of success on the mortality endpoint (Chi square test) if enrollment continues to the maximum sample size (N=2000), and all subjects are followed to their primary outcome.

Similarly, we compute predictive probabilities for the VVFD endpoint using a model based on an exponential family (additional details of the model may be found in a separate document entitled *VICTAS Trial Adaptive Design Report*):

- PP_{VVFD} (current N): the predictive probability of success on the VVFD endpoint (Wilcoxon test) if enrollment stops at the current sample size, and all currently enrolled subjects are followed to their primary outcome.
- PP_{VVFD} (max N): the predictive probability of success on the VVFD endpoint (Wilcoxon test) if enrollment continues to the maximum sample size (N=2000), and all subjects are followed to their primary outcome.

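### The 0.024 mortality test does not hold its level when only VVFD improves: mortality data help choose the final N, and a false mortality claim then occurs about 3–4% of the time

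*Combined protocol and SAP*

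**What the plan says.** Section 11.2 states: "The overall Type I error rate for the trial is controlled at 2.5" percent. Section 6.1 divides this: "The early interim analyses have conservative rules for spending alpha so that 0.1% will be used up to N=400", with the remaining 2.4% kept for N=500 or later.

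From N=500 the primary test is a Wilcoxon test of VVFD at one-sided 0.022. Section 11.4.1 explains that value: "This p-value threshold was selected through simulations in order to control type I error and account for the multiple analyses" at 500, 1000, 1500 and 2000.

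Mortality is the key secondary endpoint, tested by chi-square only if VVFD succeeds. Section 11.4.2 then says: "In that case, the mortality endpoint will be tested with one-sided alpha of 0.024". The same value applies at every possible final N, and no allowance for the later analyses is described.

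Sections 6.2 and 11.5.2 set the stopping rules at 500, 1000 and 1500. Accrual stops for success on both endpoints if the predictive probabilities at the current N exceed 95% for VVFD and for mortality. It stops for success on VVFD alone if the VVFD probability exceeds 95% and the "predictive probability for detection of such an effect on mortality (at the maximal sample size) is less than 10" percent. It stops for futility on VVFD alone. Otherwise it continues.

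**The concern.** Mortality gets one formal test, but at a sample size that the mortality data helped to pick. Once VVFD looks positive, a favourable chance result on mortality ends accrual and is kept. An indeterminate one brings 500 more subjects and another chance to cross the same 0.024. A test at a data-selected N does not keep its nominal level unless the threshold allows for the selection.

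The gate controls this only when VVFD is null, because it is then rarely open. When VVFD truly improves, the gate is open and the error rate for mortality is whatever the adaptive test delivers. The plan foresees this situation: Section 6.2.c is a rule for success on VVFD without mortality, and Section 11.2 says VVFD also reflects time on support among survivors.

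A mortality benefit is the most consequential claim the trial can make, and readers will take the stated 2.5% to cover it.

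**Working it through.** **Inputs from the plan.** VVFD threshold 0.022, mortality threshold 0.024, and the predictive-probability cut-offs above. At 200, 300 and 400, accrual stops if the predictive probability of mortality p<0.001 exceeds 90% (Section 6.2). Allocation is 1:1. The interim mortality model is beta-binomial "with independent non-informative Beta(0.5, 0.5) priors on each" arm's mortality rate (Section 11.5.1).

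**Outcomes pending at an interim.** The outcome takes 30 days, so about one month of accrual is pending.
- Section 6.4: "Enrollment of 500 subjects is predicted to require approximately 36 months after the first subject is enrolled". 500/36 ≈ 14 per month.
- Section 9.2: "It is anticipated that each site will enroll on average 2 subjects per month". With the minimum of 20 sites in Section 6.4, 20 × 2 = 40 per month.
- 80 and 120 pending are assumed, to represent data lag.

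**Other assumptions.** Equal mortality of 20–40% in the two arms (Section 3.2 gives 20–30%). A flat-prior normal approximation replaces the VVFD predictive model, which is in the separate report.

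**The plan's own figures.**
- 0.025 − 0.001 = 0.024, as stated.
- Power above 90% for a 20-point mortality difference at one-sided 0.001: 40% v 20% gives 90.4% at N=400 and 96.7% at N=500. Reproduced.
- Overall 2.5% under the global null: any success 2.1–2.7%, and a mortality claim 0.8–1.3%, in simulation B below. Roughly met.
- Alpha spend of 0.010 at N=500 (Section 11.2): simulation C gave 0.002–0.004. Not reproduced; the simulation inputs behind that table are not in the documents.

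**Mechanism, one case.** No mortality effect at 30% mortality, gate always open, 14 pending, 40,000 simulated trials:

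| Final N | Trials ending there | False mortality claim (all trials) | Rate among trials ending there |
|---|---|---|---|
| 500 | 45.65% | 1.208% | 1.208/45.65 = 2.6% |
| 1000 | 28.76% | 1.307% | 1.307/28.76 = 4.5% |
| 1500 | 16.61% | 0.887% | 0.887/16.61 = 5.3% |
| 2000 | 8.88% | 0.967% | 0.967/8.88 = 10.9% |

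Sum: 1.208 + 1.307 + 0.887 + 0.967 = 4.37%. The Monte Carlo standard error is √(0.044 × 0.956/40,000) ≈ 0.1 point. For reference, one test at a fixed N gives 2.4%, and four unadjusted looks at 0.024 with no stopping rules give 6.1%.

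**False mortality claim, VVFD effective and mortality null.**
- A: patient-level binomial, gate open, beta-binomial predictive probability, uncorrected chi-square, mortality 20/25/30%, 300,000 trials each.
- B: bivariate Brownian motion, VVFD–mortality correlation 0.65, VVFD power about 55–96%, 0.8–1 million trials per cell.
- C: patient-level with a tie-corrected Wilcoxon on VVFD, 30% mortality, 40,000 trials (VVFD simulated / taken as certain).
- D: gate open, as A, but with a continuity-corrected chi-square and mortality of 20–30%.

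| Pending | A | B | C | D |
|---|---|---|---|---|
| 14 | 4.2–4.3% | 4.0–4.2% | 4.6 / 4.4% | 3.4–3.6% |
| 40 | 3.5–3.6% | 3.5–3.6% | 3.5 / 3.5% | 3.0–3.1% |
| 80 | 3.0–3.1% | 3.1–3.2% | 3.2 / 3.0% | 2.6–2.7% |
| 120 | – | 2.9–3.0% | – | 2.5% |

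**Sensitivity.** The looks at 200–400 contribute about 0.1 point or less. Correlations of 0.5–0.8 give 4.0–4.3%, 3.5–3.7% and 3.1–3.3% for 14, 40 and 80 pending. With VVFD power of only about 13%, the gate is seldom open and the rates are 2.7%, 2.3% and 2.0%.

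**Threshold that restores control** (25% mortality, gate open): 0.0135 gives 2.42% (14 pending), 0.016 gives 2.42% (40) and 0.018 gives 2.35% (80).

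**The case against.** The 2.5% can be read as an error rate for trial success, which from N=500 means success on VVFD. Mortality is tested only afterwards and cannot add to that rate; under the global null the plan does about what it says. No passage expressly promises control of mortality claims when only VVFD works. Full operating characteristics are deferred to the Adaptive Design Report, which may give this one. The simulations here do not match the one published table entry they were compared with (0.010 at N=500), so decimals should not be over-read. The size also depends on choices the plan leaves open: the number pending, VVFD power, and whether the chi-square is continuity-corrected. Because deaths score zero VVFD, the problem needs a VVFD effect confined to survivors.

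Much of this limits precision and scope, and is accepted. It does not remove the point. Mortality sits inside the gatekeeping strategy, unlike the endpoints in Section 11.4.3 that are expressly left unadjusted. A gate gives strong control only if each test holds its level at its own stopping time. The gate-open figures need no VVFD model, so the unmatched table entry does not bear on them. Section 11.4.2 names no continuity correction, and even with one the plan's two accrual cases give 3.0–3.6%.

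**Conclusion.** The concern holds. If VVFD truly improves with reasonable power and mortality does not, the gated 0.024 test produces a false mortality claim in about 3–4% of trials: about 4.2% with 14 outcomes pending and 3.6% with 40 (the plan's two accrual figures), and 3.2% with 80 and 3.0% with 120 (assumed lag). A continuity correction would lower this to about 2.5–3.6%. If VVFD power is low, the rate is 2.0–2.7%. The 2.5% control is supported under the global null, but the documents do not support it for mortality when only VVFD works.

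The result rests on assumed mortality rates and pending counts, on an approximate VVFD predictive model where VVFD is simulated, and on a design report that could not be checked. Confidence is medium on the exact size and higher on its direction. It should be fixed, and the fix is small.

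**What to change.** Either of two changes is adequate.

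1. **Recalibrate.** Replace 0.024 in Sections 11.4.2 and 6.2.b, and in the mortality predictive probabilities, with a threshold set in the sponsor's simulator under VVFD effective and mortality null, so that the false-claim rate is at most 2.5%. The values 0.0135, 0.016 and 0.018 above are a guide only, since they depend on the number pending.
2. **Disclose.** Keep 0.024. State in Sections 11.2 and 11.4.2 that the 2.5% applies under the global null, and report the simulated mortality false-claim rate when only VVFD is effective.

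Option 2 costs wording and one reported simulation. Option 1 costs some power and subjects. At 25% v 19% mortality with VVFD success near certain:

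| Pending | Mortality power, 0.024 → recalibrated | Expected N |
|---|---|---|
| 14 | 88.8% → 84.0% | 1130 → 1226 |
| 40 | 88.1% → 84.7% | 1214 → 1281 |
| 80 | 87.4% → 85.0% | 1292 → 1337 |

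Within option 1, an O'Brien-Fleming-type mortality boundary would keep more power (87.3%, 86.9% and 86.5%) but raise expected N to 1473, 1525 and 1569. Under either option, Section 11.4.2 should also say whether the chi-square is continuity-corrected.

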11.4.3. Additional Efficacy Endpoints

The following endpoints will be analyzed as supportive evidence of treatment benefit. The tests will not be included in the gatekeeping strategy, so that type I error will not be adjusted for multiple testing:

Other outcomes Mortality at 180 days Length of ICU stay Length of hospital stay Physical, emotional and cognitive outcomes at 180 days

11.4.4. Safety Endpoints

Complete listings and summary tables for all safety information will be presented for subjects who are included in the Safety analysis set. Descriptive statistics (number and percentage) for adverse events and serious adverse events will be presented by treatment arm. No formal statistical analysis will be performed.

